11.4.2. Handling of the Difference between the Scheduled and the Actual Sampling Times

The actual clock time for dosing and each collection time for the PK samples will be recorded. For all sampling times, the actual sampling times relative to dosing will be calculated as the difference between the actual clock time of sampling and the actual clock time of dosing. The actual post-dose sampling times relative to dosing expressed in hours and rounded off to three decimal digits will be used to calculate the PK parameters, except for pre-dose samples occurring prior to dosing, which will always be reported as zero (0.000), regardless of the time difference. Scheduled sampling times will be presented in concentration tables individual and mean graphs.

11.4.3. Plasma Pharmacokinetic Parameters

Plasma concentrations from MT6 will be used to calculate the following parameters by standard non-compartmental methods.

On Day 1 and Day 7 (first 24 patients), the following PK parameters will be derived:

- C_{max}: maximum plasma concentration by direct observation from the concentration-time profile (on Day 1)
- T_{max}: Time to peak plasma concentration by direct observation from the concentration-time profile (on Day 1)

This document is confidential

Filing requirements: TMF

- C_{max ss}: maximum plasma concentration at steady-state by direct observation from the concentration-time profile (on Day 7)
- T_{max ss}: Time to peak plasma concentration at steady-state by direct observation from the concentration-time profile (on Day 7)
- AUC₀₋₄: area under the plasma concentration-time curve from zero to 4 hours post the 1st daily administration
- AUCT: area under the plasma concentration-time curve during a dosage interval (4 hours) for the 1st daily administration using linear up log down trapezoidal method (on Day 7)
- AUC_{0-t}: Area under the concentration-time curve from time zero to the last measurable concentration for the 1st daily administration using linear up log down trapezoidal method (on Days 1 and 7)
- C_{trough}: Trough plasma concentration (measured concentration at the end of a dosing interval [taken directly before next administration])

The remaining other plasma levels will only be listed and summarised and not used for any PK parameters calculations.

11.4.4. PK Parameters Summarisation

 C_{max} , C_{max} ss, T_{max} , T_{max} ss, AUC_{0-4} (Day 1), AUC_{τ} (Day 7) and AUC_{0-t} and C_{trough} will be summarised for Day 1 and Day 7 using arithmetic mean, SD, CV%, minimum, median, maximum, geometric mean, and geometric CV%.

The PK parameters will be summarised by dose level and by randomisation strata disease stage (stage 2 and stage 3) and region (North America and Europe) based on the PK population.

11.5. Planned Statistical Models for PK Parameters and Concentrations

Not applicable.

11.6. Interim Analyses

Not applicable.

11.7. Deviation from Analyses Planned in Protocol

Not applicable.

12. Safety

The population used for safety analyses will be the Safety Population (SAF). Safety will be assessed on the basis of AEs, clinical laboratory data, ECG parameters, physical examinations, further opthalomological examinations, and vital signs.

12.1. Adverse Events

Adverse events will be coded using the MedDRA coding system.

Analyses of AEs will mostly be performed for those events that are treatment-emergent, which is defined as any condition that was not present prior to the first study drug treatment but appeared following treatment.

If the start date of an AE is partially missing, the date will be compared as far as possible with the start date of study treatment. The AE will be assumed to be treatment-emergent if it cannot be definitively shown that the AE did not occur during the treatment administration period (worst case approach).

The following general rules to determine if an AE is treatment-emergent will be used:

- If the start day is missing but the start month and year are complete, an AE will be excluded only if the start month/year is before the month/year of treatment administration or if the stop date/time is before first treatment administration.
- If the start day and month are missing but the start year is complete, an AE will be excluded only if the start year is before the year of treatment administration or if the stop date/time is before first treatment administration.
- If the start date is completely missing, an AE will be considered treatment-emergent unless the stop date is before first treatment administration.

Adverse events are summarised by patient incidence rates; therefore, in any tabulation, a patient contributes only once to the count for a given SOC or PT (i.e., the most related occurrence or the most intense occurrence).

An overall AE incidence summary table will be produced and will include:

- The number and percentage of patients reporting at least 1 AE
- The number and percentage of patients reporting at least 1 Ocular AE
- The number and percentage of patients reporting at least 1 Ocular AE on study eye
- The number and percentage of patients reporting at least 1 TEAE
- The number and percentage of patients reporting at least 1 ocular TEAE
- The number and percentage of patients reporting at least 1 TEAE (by maximum intensity)
- The number and percentage of patients reporting at least 1 Serious AE (SAE)
- The number and percentage of patients reporting at least 1 ocular Serious AE (SAE)
- The number and percentage of patients reporting at least 1 serious TEAE
- The number and percentage of patients reporting at least 1 ocular serious TEAE
- The number and percentage of patients reporting at least 1 related TEAE
- The number and percentage of patients reporting at least 1 related serious TEAE
- The number and percentage of patients reporting at least 1 TEAE leading to study drug discontinuation

- The number and percentage of patients reporting at least 1 ocular TEAE leading to study drug discontinuation
- The number and percentage of patients with AEs leading to death
- The number and percentage of patients reporting at least 1 AE of special interest
- The number and percentage of patients reporting at least 1 AE due to overdose
- The number and percentage of patients reporting at least 1 AE onset during the screening period
- The number and percentage of patients reporting at least 1 ocular AE onset during the screening period
- The number and percentage of patients reporting at least 1 AE onset during the treatment administration period
- The number and percentage of patients reporting at least 1 ocular AE onset during the treatment administration period
- The number and percentage of patients reporting at least 1 AE onset during the follow-up period
 The number and percentage of patients reporting at least 1 ocular AE onset during the follow-up period

Tabulations by SOC and PT will be produced for:

- All AEs (overall and by study period: screening, treatment administration and follow-up)
- Ocular AEs, overall and stratified for eye
- TEAEs
- Ocular TEAEs, overall and stratified for eye
- TEAEs by maximum intensity
- Ocular TEAEs by maximum intensity
- SAEs, overall, non-ocular and ocular, stratified for eye
- Serious TEAEs, overall, non-ocular and ocular, stratified for eye
- Related TEAEs (related to study drug and/or study procedure)
- · Related serious TEAEs
- TEAEs leading to study drug discontinuation, overall, non-ocular and ocular, stratified for eye
- AEs leading to death
- · AEs of special interest
- AEs due to overdose

These will be presented by SOC and PT, sorted by highest frequency within SOC and PT in the Total column. The 'All AEs' table will be presented by study period (overall, screening, treatment administration and follow-up). AEs that span multiple of these periods will only be counted once in the study period of the onset of the AE.

Patient listings will be generated for all AEs, all ocular AEs, all SAEs, TEAEs, AEs of special interest, AEs leading to study drug discontinuation, AEs due to overdose, and deaths.

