10.2 Visit 1a (Screening Visit – Day -3 to Day 1)

At the Screening Visit, the patient's eligibility for study participation will be determined by checking all inclusion and exclusion criteria as specified in Section 8.

Medical history will be recorded at the Screening Visit. Investigators should document the occurrence, signs, and symptoms of all prior significant illnesses. Medical conditions ongoing at the time when informed consent is given or at the Screening Visit (Visit 1a) are to be regarded as concomitant. Medical history will include alcohol consumption and smoking history, if applicable.

Illnesses first occurring or detected during the study and/or worsening of a concomitant illness during the study are to be documented as AEs on the eCRF in accordance with Section 12.7. All changes not present at the Screening Visit or described in the past medical history and identified as clinically noteworthy must be recorded as AEs.

Additionally, demographic data will be collected for all patients and include year of birth, sex, ethnic origin (race) and iris colour.

The Screening Visit (Visit 1a) will entail the following evaluations:

- Inclusion/exclusion criteria
- Medical history
- Demographics
- Concomitant medications
- Recording of (S)AEs
- Measurement of vital signs (blood pressure and heart rate)
- Physical examination
- Measure height and weight
- Review of concomitant medications
- BCDVA both eyes
- Slit lamp examination **both eyes**

- Corneal photo without fluorescein both eyes
- Fluorescein stain test and corneal photo- both eyes
- Corneal sensitivity **both eyes**
- Fundus examination **both eyes**
- Schirmer test without anaesthesia
- Urine pregnancy test (for females of childbearing potential)

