12.7 Adverse Events

12.7.1 Adverse Events

An AE is any symptom, physical sign, syndrome, or disease that either emerges during the study or, if present at the Screening Visit, worsens during the study, regardless of the suspected cause of the event. All medical conditions (except those related to the indication under study) present at the Screening Visit will be documented in the medical history eCRF. Changes in these conditions and new symptoms, physical signs, syndromes, or diseases should be noted on the AE eCRF during the rest of the study. Clinically significant findings from laboratory assessments, vital signs measurements, ECGs, and other procedures that result in a diagnosis should also be recorded as AEs. Surgical procedures that were planned before the patient enrolled in the study are not considered AEs if the conditions were known before study inclusion; the medical condition should be reported in the patient's medical history.

Patients will be instructed to report AEs at each study visit. All AEs are to be followed up until resolution or a stable clinical endpoint is reached.

Each AE is to be documented on the eCRF with reference to date of onset, duration, frequency, severity, seriousness, relationship to study drug, action taken with study drug, treatment of event, and outcome. For ocular AEs, the eye (study eye or fellow eye) must be recorded on the eCRF as well. Furthermore, each AE is to be classified as being serious or nonserious. Changes in AEs and resolution dates are to be documented on the eCRF.

For the purposes of this study, the period of observation for collection of AEs extends from the time the patient gives informed consent until the last Follow-up Visit. Follow-up of the AE, even after the date of therapy discontinuation, is required if the AE persists until the event resolves or stabilises at a level acceptable to the investigator.

When changes in the intensity of an AE occur more frequently than once a day, the maximum intensity for the event should be noted. If the intensity category changes over a number of days, then those changes should be recorded separately (with distinct onset dates).

Specific guidelines for classifying AEs by intensity and relationship to study drug are given in Table 4 and Table 5.

Table 4. Classification of Adverse Events by Intensity

MILD: An AE that is easily tolerated by the patient, causing minimal discomfort and not interfering with everyday activities.

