15.5 Safety Analysis

All reported AEs will be coded using the Medical Dictionary for Regulatory Activities (MedDRA). The incidence of treatment-emergent AEs (TEAEs; events with onset dates on or after the start of the study drug) will be included in incidence tables. Events with missing onset dates will be included as treatment-emergent. If a patient experiences more than one occurrence of the same AE, the occurrence with the greatest severity and the closest association with the study drug will be used in the summary tables. Serious AEs and AEs causing discontinuation will be tabulated. All AEs will be listed by patient, along with information regarding onset, duration, relationship and severity to study drug, action taken with study drug, treatment of event, and outcome.

Clinical laboratory data and vital signs will be summarised using descriptive statistics, including mean values and mean change from baseline values, as well as numbers of patients with values outside limits of the normal range at each time point.

Summary tables will be provided for concomitant medications initiated during the study period.

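### The SAP's definition of a treatment-emergent AE omits worsening of pre-existing conditions and contradicts the protocol; read literally, it drops such events from the 8 TEAE tabulations

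*SAP*

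**What the plan says.** The SAP, section 12.1, defines treatment-emergent as "any condition that was not present prior to the first study drug treatment but appeared following treatment". The same sentence makes this the main filter for safety: "Analyses of AEs will mostly be performed for those events that are treatment-emergent".

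The protocol is broader in three places:

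- Section 12.7.1 defines an AE as something that "either emerges during the study or, if present at the Screening Visit, worsens during the study". It also asks sites to enter a change in intensity over days as a separate record with its own start date.
- Section 10.2 applies the same rule to concomitant disease: "worsening of a concomitant illness during the study are to be documented as AEs on the eCRF".
- Section 15.5 defines TEAEs as "events with onset dates on or after the start of the study drug", and counts events with no onset date as treatment-emergent.

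Protocol section 15 gives the SAP precedence where the two differ. SAP 2.3, which sets out the changes from the protocol, does not mention the TEAE definition.

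**The concern.** The SAP definition turns on whether the condition existed before dosing. The protocol definition turns on when the AE record starts. The two agree for new conditions and disagree for worsening of old ones. Every patient enters with Stage 2 or 3 neurotrophic keratitis in the study eye, and many may bring other ocular or systemic history, so worsening on treatment is a foreseeable kind of event in this population.

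Two programmers, each following a controlling document, could flag the same record differently. The narrowing is undeclared and looks unintended. It would show in the tables that describe how severe events were, whether they were thought related, and whether they ended treatment, all by dose.

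**Working it through.** No arithmetic on design figures applies. The check has three steps.

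**1. Classify four cases under each definition.**

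| Case | Protocol 15.5 | SAP 12.1, literal |
|---|---|---|
| A. New condition, start date complete and after first dose | TEAE | TEAE |
| B. Condition in the medical history; worsens after first dose; AE record fully dated | TEAE | Not a TEAE |
| C. AE starts mild between consent and first dose; becomes severe on treatment; second record fully dated | TEAE | Not a TEAE |
| D. As B, but start date wholly missing and stop date not before first dose | TEAE | TEAE, through the missing-date rule |

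**2. Ask whether the SAP date rules repair B and C.** They do not. The AE rules in SAP 8.3.1 and the three bullets in SAP 12.1 all begin from a missing start day, a missing start day and month, or a wholly missing start date. A record with a complete start date meets none of those conditions, so only the defining sentence applies to it. The result is perverse: D counts and the better-documented B does not. The footnotes of the TEAE table shells (for example Table 14.3.1.4) give no other definition.

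**3. Count the tables affected.** SAP 12.1 lists 14 SOC/PT tabulations.

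- Restricted to TEAEs (8): TEAEs; ocular TEAEs; TEAEs by maximum intensity; ocular TEAEs by maximum intensity; serious TEAEs; related TEAEs; related serious TEAEs; TEAEs leading to study drug discontinuation.
- Not restricted (6): all AEs; ocular AEs; SAEs; AEs leading to death; AESIs; AEs due to overdose.

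8 + 6 = 14. Maximum intensity, relatedness and discontinuation appear by SOC/PT only in the first group, so no all-AE table restores that breakdown by dose. The TEAE rows of the overall AE summary, the TEAE listing and the TEAE flag in the other AE listings depend on the same definition.

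**The case against.** The strongest reply is that little is actually hidden, and much of that reply stands.

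- A worsening entered as an AE, as the protocol requires, still appears by arm in the All AEs table (also split by study period) and the Ocular AEs table (also split by eye). The overall summary counts AEs and ocular AEs with onset during treatment.
- A severe worsening judged related to study drug is either serious, and so in the SAE table, or non-serious, and so an AESI under protocol 12.7.2. Neither table is limited to TEAEs. What is exposed is mainly worsening that is mild or moderate, or unrelated.
- AEs leading to discontinuation have a listing not limited to TEAEs (Table 14.3.2.4). Treatment discontinuations due to related AEs are counted by arm as an intercurrent event.
- Deterioration of the keratitis itself is a comparative secondary endpoint (SAP 10.3.5), and rescue is counted by arm.
- The SAP describes no step that matches AEs to medical history to remove worsened conditions. Its date rules work from the AE record, and a separate record for a change in intensity would carry a post-dose start date. A programmer may well derive the flag from onset date alone.

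These points limit the consequence. They do not remove the contradiction. The last one says only that the SAP might not be followed as written.

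A reader might infer that worsening is lost from the safety tables as a whole, that all 108 patients are exposed to misclassification, or that the affected tables are the ones used to choose the dose. The documents support none of these. Six tabulations are untouched. Having study-eye disease does not mean having a misclassified AE. The objective speaks of the best benefit-risk ratio without naming the tables that will decide it.

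**Conclusion.** The concern holds as an undeclared contradiction in a governing definition. For a fully dated AE that is a worsening of an earlier condition, the SAP's rule gives a different answer from the protocol's, and the SAP takes precedence.

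The reach is 8 of 14 SOC/PT tabulations plus the TEAE rows of the overall summary. The number of events cannot be estimated, because the documents give no expected rate of worsening. The conclusion assumes that sites record worsening as AEs, as protocol 10.2 and 12.7.1 require, and that the SAP sentence is applied literally. If the flag is programmed from onset date instead, the tables would match the protocol and only the wording would be wrong. No efficacy inference or data collection is affected. It should be corrected because the remedy is small and the tables concerned are standard safety outputs.

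**What to change.** Before unmasking, replace the defining sentence in SAP 12.1. A TEAE is an AE with onset on or after the first administration of study drug, or a pre-existing condition that worsens in intensity on or after that time.

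Add how worsening is identified: from the eCRF AE records, using the distinct onset dates that protocol 12.7.1 requires when intensity changes. For a condition held in the medical history, the post-dose AE record itself marks the worsening.

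Align the partial- and missing-date rules in SAP 8.3.1 and 12.1 with protocol 15.5, so that complete and incomplete dates lead to the same classification. Put the definition in the TEAE table footnotes. If any departure from protocol 15.5 is intended, list it in SAP 2.3.

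The cost is one or two sentences, a footnote and a check of the flag derivation. No new data are needed.

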12.2. Laboratory Evaluations

Baseline values and changes from baseline for each laboratory parameter reported in Table 10 will be descriptively summarised by treatment group and number of patients with values outside limits of the normal range at each time point will be presented. In case of multiple available results per visit and timepoint, the first will be used and esults below the lower limit of quantitation will be set equal to the LLOQ for the descriptive summary tables. All data will be listed as collected.

Table 10: Clinical Laboratory Parameters

Hematology	Biochemistry
Red blood cells	Albumin
White blood cells	Alanine aminotransferase
Neutrophils	Aspartate aminotransferase
Lymphocytes	Alkaline phosphatase
Monocytes	Blood urea nitrogen
Eosinophils	Creatinine
Basophils	Sodium
Haematocrit	Potassium
Haemoglobin	Chloride
Mean corpuscular haemoglobin	Calcium
Mean corpuscular haemoglobin concentration	Phosphorus
Mean corpuscular volume	Gamma-glutamyl transpeptidase
Platelet count	Glucose
Other	Lactate dehydrogenase
	Total bilirubin
	Direct bilirubin
	Total cholesterol
	Triglycerides
	Other

12.3. Vital Signs

Vital signs (systolic and diastolic blood pressure, heart rate), including the change from baseline, will be presented in a summary table for all treatment groups by visit, and all data (including height and weight) are presented for each patient in a listing.

12.4. ECG

The 12-Lead ECG findings will be presented in a by-patient listing. ECG assessments were only performed in the first 24 patients of cohorts 1 to 3 as the IDMC decision in the first formal meeting was to drop the ECG assessments from the list of scheduled study assessments for all patients enrolled in the cohort 4.

12.5. Physical Examination

All physical examination findings will be presented in a by-patient listing.

12.6. Other Safety

12.6.1. Opthalmological Safety Examination

All findings from the slit lamp examin ation (except from the cornea) of the study eye and the fellow eye will be listed.

12.6.2. Fundus Examination

All data from the fundus examination of the study eye and the fellow eye will be listed.

13. Interim Analyses

No formal interim analysis is planned.

Sponsor: Recordati Rare Diseases; Protocol No.: REC0559-B-001

14. Reference List

Cochran, WG. 1954. Some Methods for Strengthening the Common Tests. Biometrics, 10, 417–451.

Mangione, CM. Version 2000. The National Eye Institute 25-Item Visual Function Questionnaire (VFQ-25): NEI VFQ Scoring Algorithm – August 2000.

Wilson, EB, Hilferty, MM 1931. The distribution of chi-square. Proceedings of the National Academy of Sciences of the United States of America 17, 684-688

15. Programming Considerations

Computer-generated output will adhere to the following specifications. The standard operating procedures (SOPs) of Syneos Health Clinical will be followed in the creation and quality control of all tables, listings and figures.

PK parameters are calculated with Phoenix® WinNonlin® version 8.3.4 (Certara USA, Inc., Princeton, NJ).

15.1. General Considerations

- Every TLF program creates only one output. Macros can be used within multiple TLF programs
- Every TLF program creates one RTF and XML file. If inferential statistical methods are used then
 also a separate detailed output of the SAS procedures referred to as 'stat output' will be created as
 well.
- · Numbering of TLFs will follow ICH E3 guidance

